8.3 Assessments by Visit

8.3.1 Baseline/Screening (within 3 months of scan):

- Informed consent: investigators or their designees will discuss with subjects the nature of the study, its requirements, risks, and restrictions to obtain informed consent for participation in the study. Subjects should have sufficient time to review the study information and consent form and to ask any questions necessary to make an informed decision regarding their participation in the study. Written informed consent is to be obtained before any other study-specific procedure.
- Eligibility criteria: make sure patient meets study eligibility criteria.
- Medical history: includes past medical history, past surgical history, allergies, any ongoing medical conditions, and including medications noted in patients record at time of screening. This can be collected from medical records.
- Quality of Life Assessments (see study calendar):

8.3.2 Imaging

- Eligibility criteria: ensure subject continues to meet study eligibility (if longer than 60 days since screening)
- Medical history: capture additional medical history since screening (if longer than 60 days since screening)
- Concomitant medications: record medications taken since screening through day of surgery (if longer than 60 days since screening)
- ^{68}Ga -PSMA-11 PET-CT:
 - Patient receives a ~3-5 mCi dose of ^{68}Ga -PSMA-11. (A physician-sponsored IND has been successfully obtained)
 - Patient will undergo research Vision PET-CT at Goodman Hall which is anticipated to last approximately 60 minutes (or similar scanner). Per our institutional standard of care, patients will receive intravenous iodinated contrast with the PET-CT unless medically contraindicated.

Imaging Protocol for ^{68}Ga -PSMA-11 PET Data Acquisition

Time (minutes)	Activity
- 60	Patient arrives, and completes consent forms, while radiopharmaceutical synthesis and quality control procedures are completed.
-5-0	Dual Energy CT for Attenuation Correction
0	Start PET/CT acquisition and administer ^{68}Ga -PSMA-11, 3-5 mCi (inside the camera).
0-60	Flow motion list-mode acquisition of PET data, allowing reconstruction of static images of radiopharmaceutical distribution over various time windows, as well as tracer kinetic modeling to determine whether and how regional pharmacokinetics are affected by the underlying regional (patho)physiology.
60-65	Contrast-CT to assist in prostate segmentation from the PET acquisition for fusion to both the mpMRI and the lesion mapping from whole-mount pathology. (Contrast CT will be omitted, if contrast agent is contraindicated based on standard clinical criteria for contrast administration.)
65	Patient can leave camera and depart.

- Reconstruction of static images showing the distribution of radioactivity in the pelvis in various time windows (e.g., 3-7 minutes; 10-15 minutes; 20-30 minutes; 40-55 minutes) to examine definition of the location and extent of prostate cancer.
- Input function formation for multi-parametric PET analysis: The input function will be generated by placing a 3D volume-of-interest in left atrium / left ventricle blood pool of the heart. The input function frame sequence will consist of 12x5s followed by 9x10s frames during the peak and a 150 s frame at 7.5 minutes, a 300 s frames at 15, 30, and 55 minutes.

Alternatively, we will also assess characterization of the input function will be generated by placing a 3D volume of interest over the abdominal aorta (possibly including the bifurcation) to capture the needed measures of blood pool radioactivity.

- The PET read will be done by a board-certified nuclear medicine specialist (e.g. [name] or similar) and the MRI read will be done by a board certified MR radiologist (e.g. [name] or similar). Suspicious lesions will be marked in a blinded fashion.
- AE assessment: AEs will be assessed at the time of ⁶⁸Ga-PSMA-11 administration any event **not expected** is collected including but not limited to: rash and shortness of breath.
- Safety monitoring following radiopharmaceutical administration will consist of visual and verbal monitoring of the patient after injection, and during and at the conclusion of the PET/CT procedure, with any apparent patient abnormalities, reactions or reported effects noted in the study records.
- The nuclear medicine technologists administering the radiopharmaceutical are responsible for immediately reporting any adverse or unexpected events to the principal investigator or clinical designee, who will report the occurrence of any adverse events to the IRB.
- As in most clinical nuclear medicine procedures, these radiopharmaceuticals are administered at a sub-pharmacologic doses. Adverse events are exceedingly unlikely, as ⁶⁸Ga-HBED-CC has been clinically employed, extensively and without reported incident, in clinical patient diagnostic imaging studies in prostate cancer patients in Germany and other European countries, as well as in over 400 patients locally.

- If there is a discrepancy between the PSMA and conventional MRI scan, the investigators will discuss the treatment plan with the patient at the investigator's discretion. This will be completed through a pre-surgery clinic or virtual visit within 9days of the PET/CT scan.

8.3.3 Surgery and Pathology

- The standard of care surgical procedure is performed as indicated by the cancer.
- Pathologic assessment: whole mount sections of prostate tissue and routine sections of lymph nodes if applicable will be fixed and analyzed by licensed pathologist per routine care. This typically happens within 2 weeks of prostatectomy.
- Additional study-related pathologic assessment: intraprostatic lesion-based assessment will be done to document the % Gleason pattern 3, 4, and 5 within each lesion. The Extra-prostatic extension and positive margins will be documented. This may be “batched” at the discretion of the pathology department.
- How the knowledge of the PSMA-PET informs treatment will be tracked. Examples of informing the decision include the number and location of ⁶⁸Ga-PSMA-PET detected: additional intraprostatic cancer lesions diagnosed, extra-prostatic extension, seminal vesicle invasion, and lymph node invasion.

9 STUDY WITHDRAWAL/DISCONTINUATION

Subjects must be discontinued from the study for the following reasons:

- Withdrawal of consent
- Investigator deems withdrawal necessary at any time if it is determined that it is not in the subjects best interest to continue, or if the subject is found to be noncompliant with study procedures.

If subject discontinues after administration of study drug, he or she will be encouraged to continue on study for safety procedures per protocol. Reason(s) for discontinuing must be clearly documented in the appropriate source documents.

10 STATISTICAL CONSIDERATIONS

10.1 Study Design

A prospective, single arm, pilot study for evaluating the performance of PSMA-PET

10.2 Study Population

The enrolled population comprises all patients who meet the eligibility criteria and are registered onto the study.

10.3 Sample Size

The sample size justification of the pilot study is based on the primary objective of estimating the sensitivity and specificity for PSMA-PET for detecting extra-prostatic extension of cancer at the nerve bundles. The sensitivity and specificity will be calculated using both the left and right nerve bundles, based on the gold standard of whole-mount pathology. A sample size of 50 patients would therefore generate 100 data points. Assuming about 20% of the 100 left and right nerve bundles are not evaluable. Then we could have at least 80 data points.

Based on the preliminary data, the prevalence of extra-prostatic extension is about 35%. The sensitivity of PSMA-PET is anticipated to be 90%. A sample size of 80 would provide a two-sided 95% sensitivity confidence interval with a width of at most 0.23. The specificity of PSMA-PET is anticipated to be 76%. A sample size of 80 would provide a two-sided 95% specificity confidence interval with a width of at most 0.25. All calculations will be based on the simple asymptotic method with continuity correction.

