^{68}Ga -PSMA-11 PET for Diagnosis and Surgical Planning. We recently published an observational trial evaluating ^{68}Ga -PSMA-11 PET-CT or PET-MRI preoperatively in 15 patients with biopsy-proven *high or intermediate-risk* prostate cancer (Bahler, et al. 2019). The PSMA-PET exam was obtained prior to scheduled surgical resection for correlation of imaging findings with whole-mount pathology. All staging ^{68}Ga -PSMA-11 PET/CT scans (15/15) showed suspicious prostate lesions (index lesion) with median (IQR) SUV of 10.0 (6-13); benign prostate had a median (IQR) SUV_{max} of 2.2 (2-3). Good registration was seen between PSMA-PET and whole mount imaging for lethal cancer. For secondary lesions, 8/11 (82%) were detected with ^{68}Ga -PSMA-11 PET; the three missed lesions were of $\leq 10\%$ Pattern 4 ($> 90\%$ pattern 3). Our study was published with the following Editorial Comment: *"This study is...one of the few that has done so for intermediate risk disease and it delineates the accuracy of PSMA imaging to differentiate histological grade groups 1- 3. Prospective well-designed trials validating PSMA imaging in these low prevalence populations are critical and a logical next step based on these study results"* (Emmett and Hofman, 2020).

Figure 2. A lesion at the base of the prostate is seen (30% pattern 4) with ^{68}Ga -PSMA-11 PET-CT scanner.

^{68}Ga -PSMA-11 PET for predicting extra-prostatic extension. Currently, we have 33 prostatectomy cases (each case has right and left nerve bundle) available with preoperative PSMA-PET imaging. Extra-prostatic extension was noted in 26/66 (39%) nerve bundles, and this was predicted in 24/26 (92%) of the cases on PSMA-PET. The PSMA-PET would have changed the treatment plan in 18/33 (55%) of cases, including choosing to spare 12 nerve bundles, while also avoiding nerve sparing in 4 cases of extra-prostatic extension. See **Appendix A** for example PSMA-PET surgeon's report to guide resection.

Prostatectomy carries significant risk for post-treatment urinary and erectile dysfunction. PSMA-PET imaging offers the potential of both cancer control and excellent quality of life for patients whose disease is localized to the prostate. There is an immediate clinical need for validation of advanced imaging (PSMA-PET) in the context of enabling more precise surgical guidance.

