10.5 Analysis of Primary Objective

The sensitivity and specificity will be summarized along with 95% CI using the simple asymptotic method with continuity correction. PPV and NPV will also be summarized along with 95% CI using the simple asymptotic method with continuity correction.

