10.6 Analysis of Secondary Objectives

The frequency of proper treatment changes directed by PSMA-PET compared to MRI will be summarized along 95% CI for all evaluable subjects, and separated for 3 areas important for genito-urinary function including: 1) Bladder neck, 2) Nerve bundles, 3) Urethral Sphincter (Figure 4). We will use the McNemar test to compare the sensitivity and specificity values between PET and MRI although data from this pilot study is considered hypothesis generating only due to the small sample size.

The quality of life data including IIEF-15 (Erectile function score), EPIC-26 (Pad use), SF-36 (overall mental and physical health domains) are longitudinal data, which will be analyzed separately. The analysis will start with the graphical representation of the data, where

mean and the standard of mean at each time point will be plotted and linked over time. An exploratory statistical modelling approach will be conducted to analyze the change over time. In particular, a mixed effects model will be used to analyze the data.

The parametric kinetic modeling data will be assessed for goodness-of-fit of the measured regional tissue time-activity curves to the applied kinetic model. Additionally, the images derived by voxel-wise kinetic modeling will be visually compared to standard reconstructions of the integrated regional concentration of radioactivity, assessing apparent lesion size, lesion position, and lesion/background contrast.

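### The primary sensitivity and specificity intervals, and the planned widths, treat two nerve bundles per patient as independent; with positive within-patient correlation they are somewhat too narrow

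*Combined protocol and SAP*

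**What the plan says.** Section 10.3 defines the unit: "The sensitivity and specificity will be calculated using both the left and right nerve bundles, based on the gold standard of whole-mount pathology". It then counts bundles: "A sample size of 50 patients would therefore generate 100 data points". The allowance for loss is also made per bundle: "Assuming about 20% of the 100 left and right nerve bundles are not evaluable". That leaves 80 bundles. With an assumed prevalence of extra-prostatic extension (EPE) of 35%, sensitivity of 90% and specificity of 76%, the section gives two-sided 95% interval widths of at most 0.23 and 0.25.

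Section 10.5 carries the same method into the primary analysis: "The sensitivity and specificity will be summarized along with 95% CI using the simple asymptotic method with continuity correction". PPV and NPV are handled in the same way.

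The preliminary data in section 3.1 have the same paired structure: "we have 33 prostatectomy cases (each case has right and left nerve bundle) available with preoperative PSMA-PET imaging". They too are reported pooled over bundles: "Extra-prostatic extension was noted in 26/66 (39%) nerve bundles".

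For the secondary comparison, section 10.6 says "We will use the McNemar test to compare the sensitivity and specificity values between PET and MRI". It gives neither the version of the test nor the unit. The only model in the plan that handles repeated observations on a patient is the mixed model in 10.6, which is for quality of life.

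**The concern.** A one-sample binomial interval is valid when the observations are independent. Here each patient can contribute two. Both bundles are imaged in one scan, read together and judged on one prostatectomy specimen. On the reading, section 8.3.2 says only "The PET read will be done by a board-certified nuclear medicine specialist". A poor scan, a reader's threshold or a feature of the tumour's tracer uptake could make PET right or wrong on both sides at once.

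If so, 80 bundles carry less information than 80 independent observations, and the primary 95% intervals cover the true value less often than stated. Estimation precision is the only justification given for the sample size, so these intervals are the trial's main inferential result.

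**Working it through.** **1. The plan's own widths.** Inputs from section 10.3: 80 bundles, prevalence 0.35, sensitivity 0.90, specificity 0.76. The Wald half-width with continuity correction is 1.96 × √(p(1−p)/n) + 1/(2n).

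- Sensitivity: n = 80 × 0.35 = 28. Half-width = 1.96 × √(0.09/28) + 1/56 = 0.111 + 0.018 = 0.129. The interval is 0.771 to 1.029, so the width is 0.258, or 0.229 with the upper limit cut at 1.
- Specificity: n = 80 × 0.65 = 52. Half-width = 1.96 × √(0.1824/52) + 1/104 = 0.116 + 0.010 = 0.126. The width is 0.251.

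These match the stated 0.23 and 0.25. Two alternatives do not: omitting the continuity correction gives 0.222 and 0.232 (untruncated), and using 80 as the denominator gives 0.144 and 0.200. The plan therefore contains no hidden allowance for clustering.

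**2. Widths with correlation.** The following are assumptions, not figures from the documents: rho, the within-patient correlation of PET correctness, from 0 to 0.6; left-right correlation of EPE status, c, from 0 to 0.2; and the 20% of bundles lost at random, bundle by bundle. Only pairs with the same EPE status contribute to a given interval, so

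design effect = 1 + rho × 0.8 × P(other bundle has the same EPE status),

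where 0.8 is the chance that the other bundle is evaluable. For a positive bundle the last term is 0.35 + 0.65c, which is 0.35 to 0.48. For a negative bundle it is 0.65 + 0.35c, which is 0.65 to 0.72.

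| | Sensitivity | Specificity |
|---|---|---|
| Design effect, rho 0.1 to 0.6 | 1.03 to 1.23 | 1.05 to 1.35 |
| Effective n (from 28 and 52) | 27 to 23 | 49 to 39 |
| Width (from 0.229, cut at 1, and 0.251) | about 0.23 to 0.245 | about 0.26 to 0.29 |

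The specificity width is 0.257 to 0.289 if only the standard error is inflated, and 0.258 to 0.295 if the continuity term also uses the effective n.

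**3. Coverage.** Simulation with 50 patients, 20% random bundle loss, c = 0.2 and 20,000 replicates per cell. Coverage of the nominal 95% interval (%):

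| rho | Planned, sensitivity | Planned, specificity | Clustered Wilson, sensitivity | Clustered Wilson, specificity |
|---|---|---|---|---|
| 0 | 93.2 | 95.3 | 96.5 | 95.8 |
| 0.1 | 92.3 | 94.5 | 96.6 | 95.2 |
| 0.2 | 92.0 | 94.1 | 96.4 | 95.2 |
| 0.4 | 91.1 | 93.0 | 96.2 | 94.9 |
| 0.6 | 90.2 | 91.5 | 96.1 | 94.7 |

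The clustered Wilson interval is the one set out under the fix. Its mean widths are 0.23 to 0.25 for sensitivity and 0.23 to 0.26 for specificity. From rho 0 to 0.6 the planned interval loses 93.2 − 90.2 = 3.0 points for sensitivity and 95.3 − 91.5 = 3.8 points for specificity.

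**4. McNemar test.** Null simulation on EPE-negative bundles, with an assumed 30% discordance and within-patient correlation of 0, 0.2, 0.4 and 0.6. Rejection at a nominal 5% is 4.9, 6.4, 7.6 and 8.8% for the uncorrected test, and 2.8, 3.9, 4.7 and 6.1% for the exact test. A patient-clustered version stays at 4.7 to 5.1%. Whether there is a problem therefore depends on the version, which the plan does not name.

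**The case against.** The omission is not in dispute; its importance is. Five points deserve weight.

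- **The direction is assumed.** No correlation is reported, and at rho 0 the planned widths are right. This stands, so the conclusion is conditional. The range is also not a bound: if bundles were lost by whole patient, the factor 0.8 would become 1 and the effect would be somewhat larger.
- **For sensitivity, the main fault is the Wald method.** An ordinary Wilson interval with no clustering adjustment covers sensitivity 94.4 to 96.0% for every rho from 0 to 0.6. This stands. It does not help specificity, where the plain Wilson interval falls to about 91.6% at rho 0.6.
- **A simpler repair may do.** A clustered Wald interval that keeps the protocol's continuity correction covers specificity 94.4 to 95.4%. This also stands, but for sensitivity it reaches only 91 to 93%, and only 86 to 89% without the correction.
- **The data will say little about rho for sensitivity.** Section 3.1 reports 24 of 26 positive bundles detected, so two misses. The trial expects about three misses in 28 (28 × 0.10 = 2.8). An estimated design effect for sensitivity will be noisy, which is a reason to floor it at 1.
- **The effect is small.** The synopsis enrols 55. At the same evaluable rate, that gives 88 bundles, and the widths at rho 0.2 are about 0.227 and 0.252, close to those stated. This is a pilot with no decision threshold. But extra patients narrow an interval; they do not restore the coverage of one that ignores clustering.

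**Conclusion.** The concern holds. The plan counts two bundles per patient as independent, both in the sample size and in the primary analysis, and nowhere adjusts for it. That follows from the text and from the reproduction of the stated widths.

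The consequence is conditional on positive within-patient correlation, which is plausible but undocumented. It is modest: with at most two bundles per patient the design effect cannot exceed 2, and under the assumptions above it stays at or below 1.35. It falls mainly on specificity, because more of the negative bundles have a partner of the same status. The point estimates are unaffected.

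This should be fixed because it concerns the error bars on the primary endpoint and the repair is cheap. The McNemar point is missing detail in a comparison that section 10.6 itself treats as exploratory.

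**What to change.** **Section 10.5.** Keep the bundle-level point estimates. Compute the intervals for sensitivity, specificity, PPV and NPV with the patient as cluster:

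1. For each measure, let m be the number of a patient's bundles in the denominator and x the number of those that are correct. The estimate is p = Σx/Σm, with n = Σm.
2. Take the ratio-estimator variance Σ(x − p·m)²/n², with the usual small-sample factor K/(K−1) for K contributing patients. Divide by p(1−p)/n to get the (Rao-Scott) design effect. Floor it at 1, and set it to 1 if p is 0 or 1.
3. Report the Wilson interval with n replaced by n divided by the design effect.

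This addresses the clustering and the Wald under-coverage for sensitivity together. Its coverage was checked for sensitivity and specificity only; PPV and NPV should be checked before the wording is fixed. A patient-level bootstrap or GEE would also address the clustering, but its coverage at about 28 positive bundles should be checked first.

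**Section 10.3.** Restate the widths over a stated range of rho that includes 0. Cross-tabulate left against right in the 33 preliminary cases to inform the range, chiefly for specificity. Say whether the upper limit is cut at 1, since the stated 0.23 depends on it.

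**Section 10.6.** State the unit and the version of the McNemar test, preferably a patient-clustered version or a paired GEE.

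**Cost.** Some SAP wording and a few lines of code, with no more patients. If rho is above 0, the stated precision becomes slightly less favourable.

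### Do the confidence interval widths of at most 0.23 and 0.25 in section 10.3, and the 35% prevalence behind them, need correcting?

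*Combined protocol and SAP*

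**What the plan says.** Section 10.3 starts from 50 patients and 100 nerve bundles. It allows for losses ("Assuming about 20% of the 100 left and right nerve bundles are not evaluable") and concludes "Then we could have at least 80 data points". It then sets three planning values:

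- Prevalence: "Based on the preliminary data, the prevalence of extra-prostatic extension is about 35" per cent.
- Sensitivity: "The sensitivity of PSMA-PET is anticipated to be 90" per cent, followed directly by "A sample size of 80 would provide a two-sided 95% sensitivity confidence interval with a width of at most 0.23".
- Specificity: "The specificity of PSMA-PET is anticipated to be 76" per cent, followed directly by "A sample size of 80 would provide a two-sided 95% specificity confidence interval with a width of at most 0.25".

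The method is given last: "All calculations will be based on the simple asymptotic method with continuity correction". Section 10.5 uses the same method for the final intervals.

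Two other places bear on the point. The preliminary data in section 3.1 report extra-prostatic extension (EPE) in 26 of 66 bundles (39%). The synopsis gives an enrolment of 55, five more than the 50 used in section 10.3.

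**The concern.** Precision is the only argument for the sample size, so the two widths carry the whole justification. Three things look wrong.

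1. The phrase *at most* suggests a guarantee. The width of a Wald interval depends on the observed proportion and on how many bundles turn out EPE-positive or EPE-negative, and the design fixes neither.
2. The formula named in the section gives 0.258 for sensitivity unless the upper limit is cut at 100%, and the section does not mention the cut.
3. The 35% is said to come from preliminary data, but the only per-bundle figure in the documents is 39%. More positives mean fewer negatives, so the specificity interval becomes wider than stated.

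If the widths had been badly understated, the trial could end with estimates too imprecise to plan a follow-on study, and the sample size would need to be revisited.

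**Working it through.** **Inputs.** From section 10.3: 80 evaluable bundles, prevalence 0.35, sensitivity 0.90, specificity 0.76, two-sided 95%, Wald interval with continuity correction. From section 3.1: prevalence 26/66 = 0.394. From the synopsis: 55 patients.

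**Formula.** Limits = p ± h, where h = 1.96·√(p(1−p)/n) + 1/(2n), cut at 0 and 1.

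**Step 1: reproduce the plan's figures.** The split is 0.35 × 80 = 28 positive and 52 negative bundles.

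- Sensitivity: h = 1.96·√(0.90·0.10/28) + 1/56 = 0.1111 + 0.0179 = 0.1290. Limits are 0.771 and 1.029. The width is 0.258 uncut and 1 − 0.771 = 0.229 cut at 1, which matches 0.23.
- Specificity: h = 1.96·√(0.76·0.24/52) + 1/104 = 0.1161 + 0.0096 = 0.1257. Limits are 0.634 and 0.886. The width is 0.2514, which matches 0.25 to two decimals.

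Other versions do not give this pair. Without the continuity correction the widths are 0.211 (cut) and 0.232. With 80 as each denominator they are 0.144 and 0.200.

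**Step 2: is *at most* a ceiling on the observed width?** No. Widths at nearby results with the 28/52 split:

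| Sensitivity result | Width | Specificity result | Width |
|---|---|---|---|
| 26/28 | 0.185 | 40/52 | 0.248 |
| 25/28 | 0.240 | 39/52 | 0.255 |
| 24/28 | 0.290 | 38/52 | 0.260 |

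The width falls below the stated value for estimates above the planning values and exceeds it for estimates below them.

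**Step 3: how often, and by how much?** Exact enumeration, with the EPE count binomial (80, 0.35), correct calls binomial given that count, and bundles independent:

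| | Sensitivity | Specificity |
|---|---|---|
| Chance of meeting the stated limit (0.23; 0.25) | 53% | 50% |
| Same, allowing for rounding (0.235; 0.255) | 57% | 59% |
| Mean width | 0.217 | 0.249 |
| Median width | 0.224 | 0.251 |

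The stated figures sit close to the centre of what the trial would deliver.

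**Step 4: prevalence of 39% instead of 35%.** With 80 bundles the split is 80 × 26/66 = 31.5 positive and 48.5 negative.

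- Sensitivity width: 0.221, narrower by 0.229 − 0.221 = 0.008.
- Specificity width: 0.261, wider by 0.261 − 0.251 = 0.010.

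**Step 5: the enrolment in the synopsis.** Assume the same 20% loss: 55 × 2 × 0.80 = 88 bundles, split 34.7/53.3 at 39%. The widths are 0.214 and 0.248, both within the stated limits.

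**The case for a change.** The strongest case for a correction is that a limit missed in over 40% of trials under the plan's own assumptions, even after allowing for rounding, cannot be called *at most*. The conditions that would make it true are not spelled out, and neither is the cut at 100%. The prevalence point does not depend on how that phrase is read: at 39% and 80 bundles the specificity width is 0.261 at the anticipated value itself. Rewording a few sentences would cost almost nothing.

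Part of this stands. The widths are not ceilings on the observed intervals, the cut at 100% is unstated, and 35% and 39% do differ. What does not follow is that the plan misleads in a way that matters:

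- Each width comes straight after its anticipated value and after a floor of 80 bundles. Read in that order, *at most* means that with those values held fixed, more bundles can only narrow the interval.
- Sensitivity cannot exceed 100%, so cutting the limit there is ordinary reporting.
- The 35% is stated as approximate. A 95% Wilson interval for 26/66, treating bundles as independent, runs from about 29% to 51%, so 35% is well supported by the same data. The 76% specificity does not appear in section 3.1 either, so section 10.3 may rest on a preliminary summary that is not printed. That is inference, but the documents do not show that the 35% was misattributed.

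**Conclusion.** No change is needed. The 0.23 and 0.25 are correctly computed planning values, not bounds on what will be observed. A statistician reading section 10.3 will take them that way, because the anticipated values stand beside them.

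The size of the issue is small. Mean widths under the plan's assumptions are 0.217 and 0.249. The prevalence difference moves the widths by about 0.01, in opposite directions. The one excess it creates (0.261 against 0.25) arises at the 80-bundle floor and disappears at 88 bundles. Nothing downstream depends on the figures: this is a single-arm pilot that estimates sensitivity and specificity, no success threshold is tied to width, and section 10.5 reports the intervals obtained. Rewording would leave enrolment, design, analysis and conclusions as they are.

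The conclusion rests on three assumptions: true values near 90% and 76%; a loss of about 20% of bundles, applied to 55 patients for the 88-bundle figure; and independence of the two bundles within a patient, which the plan's own formula also assumes.
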